5.1 Primary endpoint

Rate of MACE (all- cause death or survived sudden cardiac arrest, myocardial infarction, re-hospitalisation for acute coronary syndrome, acute unplanned PCI, coronary artery bypass grafting (CABG) and documented life-threatening arrhythmias (VF, VT, AV-block III)) within 30 days Copeptin vs. Control group

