and 6-9 hours later. Thus, patients with a positive Troponin at baseline belong to a well defined patient group which can be treated according to standard guidelines. Unfortunately, in a population of patients with suspected acute coronary syndrome less than a quarter of the patients is tested positive for Troponin at presentation to the Emergency Department. In a chest pain evaluation by Newby et al. 1005 patients without ST-segment elevation in 6 chest pain units were tested for various cardiac biomarkers. At baseline, 13.7% of patients were positive for Troponin I, after serial testing this number grew to 26% [3]. In a trial performed by our site we enrolled 429 patients with suspected acute coronary syndrome of which 23.8% were initially Troponin I positive, including patients with ST-segment elevation [1]. In both trials the majority of patients were Troponin negative. It is one of the big challenges in Emergency Medicine to decide on whether a Troponin negative chest pain patient should be admitted to hospital for urgent catheterization, admitted to hospital for further evaluation and possibly later cardiac catheterization or should be discharged home for further ambulatory evaluation and care.

Pope et al. assessed the incidence of missed diagnoses of acute cardiac ischemia in the Emergency Department by analysing data from 10.689 patients with chest pain suggestive of acute coronary syndrome. 2.1 % of patients with acute myocardial infarction and 2.3% of patients with unstable angina were mistakenly discharged from the ED [4]. Given the huge impact this may have on the patient's life this is an unacceptably high number. On the other hand, fear of this potentially fatal error means that a large number of patients are being classified as suspected acute coronary syndrome and are therefore admitted to hospital for serial biomarker testing, monitoring and initialisation of medical treatment despite the absence of an acute illness. These patients are put at an unnecessary risk of side effects from the antithrombotic and anticoagulant medication which they receive as standard care for the duration of their ACS evaluation.

A new cardiac biomarker that provides "rule-out" information in a sense that patients at low risk can be identified straight after admission to the Emergency Department and can safely be transferred to ambulant care is highly sought after.

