5 Study objectives

This is a multicentre biomarker randomized controlled trial to quantify the benefit of integrating the new biomarker Copeptin into the process of managing patients with suspected non ST-elevation acute coronary syndrome (N-STEACS) with a negative baseline Troponin I test result in the Emergency Department and Chest Pain Unit.

Hypothesis:

Patients with suspected ACS with a negative baseline Troponin who test negative for Copeptin at admission are at low risk of ACS and can safely be discharged into ambulant

care. These patients will not experience a higher rate of MACE within 30 days after their admission than patients who are managed by standard practise of care.

Secondary hypotheses:

Patients with suspected ACS with a negative baseline Troponin T who test positive for Copeptin at admission are at risk for ACS and should be evaluated as by standard of care. The Integration of Copeptin into the CPU process will shorten the patient's length of Emergency Department/ CPU and hospital stay and will improve patient satisfaction

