5.2 Secondary endpoints

5.2.1 Secondary efficacy endpoints

Rate of Patients in whom coronary angiography is performed

Rate of Patients with PCI after Index CA

Rate of Patients with CABG after Index CA

Other cardiovascular diagnoses found in index CA

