7.1 General Patient Flow

Consecutive N-STEACS patients of the Chest Pain Unit with a negative Troponin T at admission will be invited to participate. Troponin T is tested as part of the standard management of patients with suspected acute coronary syndrome. Patients who give their written informed consent will be randomized into one of two study arms (experimental and standard management).

Experimental Arm: Further management dependent on Copeptin result

1. Patients of the above described characteristics who test **negative for Copeptin** at admission will be considered low-risk. In these patients we abstain from further ACS evaluation and instead discharge them into ambulant care. Before discharge patients will have a final visit to secure their well-being. The visit includes a physical examination, an ECG and an assessment for MACE and bleeding events.

Patients who show any signs and symptoms of an acute illness requiring in-hospital treatment will not be discharged (see withdrawal criteria 5.3). This decision is at the discretion of the attending physician.

To secure the patients safety they will be discharged into each co-operating network of resident cardiologists . Patients are to see a cardiologist within a maximum of 3 days after discharge (if discharge falls on a Friday), preferably on the next day after discharge. Further appointments will be at the discretion of the resident cardiologist (see 7.2).

2. Patients with the above described characteristics who test **positive for Copeptin** at admission will be managed as by standard practice i.e. patients will be evaluated as by standard of care abiding current guidelines for the management of patients with suspected ACS

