8.6 Clinical processes

Procedure	Screening	Enrolment	Randomization	Discharge	30d	90d
Screening Log	x					
Medical history	x					
Physical exam.	x					
Routine -ECG	x					
Blood routine*	x					
Copeptin		x**				
Informed consent		x				
Copeptin result request			(x) ***			
Questionnaire contentedness				x		
MACE and bleeding event assessment				x	x	x

- Including Troponin and CK

**request from routine blood sample from screening period

*** only for patients in experimental group

All in-hospital examinations are standard practice of care in patients with suspected ACS. The deviations concern the process of patient management – early discharge of Copeptin negative patients and further evaluation of high-risk ACS of Copeptin positive patients - rather than in-hospital examinations. All CPU patients are under constant monitoring and risk assessment.

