8.7 Follow-up

All patients will have a 30-day and a 90-day follow-up. Both follow-ups are telephone visits to assess:

- Survival
- MACE and bleeding complications

In case of death or hospitalization during the study period medical records will be requested. The patient will consent to this in the informed consent form.

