11.1 Definition

Major adverse cardiac event (MACE) is defined as

- All- cause death or survived sudden cardiac arrest
- myocardial infarction
- Re-hospitalisation for acute coronary syndrome
- Acute unplanned PCI
- Coronary artery bypass grafting (CABG)
- Documented life-threatening arrhythmias (VF, VT, AV-block III)

Major bleeding is defined as

- Non-CABG intracranial, intraocular, or retroperitoneal bleeding
- Access-site hemorrhage requiring intervention or resulting in a ≥ 5 cm diameter hematoma
- Reduction in hemoglobin concentration of ≥ 4 g/dL without or ≥ 3 g/dL with an overt bleeding source
- Reoperation for bleeding
- Blood product transfusion

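### Primary MACE counts any infarction and any CABG from admission, but discharged copeptin-negative patients skip the work-up that detects them; this can favour a finding of safety, though the net direction is not established

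*Protocol*

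**What the plan says.** Section 5.1 lists, among the MACE components, "myocardial infarction, re-hospitalisation for acute coronary syndrome, acute unplanned PCI, coronary artery bypass grafting (CABG"). Section 11.1 repeats the list, with "Coronary artery bypass grafting (CABG") standing alone; only PCI is restricted to acute, unplanned procedures.

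The clock starts at admission. Section 5 states the hypothesis as "These patients will not experience a higher rate of MACE within 30 days after their admission" than patients under standard care. The schedule in 8.6 places "MACE and bleeding event assessment" at discharge, 30 days and 90 days, so in-hospital events are collected. For the later two time points, 8.7 says: "Both follow-ups are telephone visits to assess" survival, MACE and bleeding.

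For copeptin-negative patients in the experimental arm, 7.1 says: "In these patients we abstain from further ACS evaluation and instead discharge them into ambulant care". Their final visit consists of an examination, an ECG and an event check; no second troponin is listed. Copeptin-positive patients (7.1) and controls (7.5) have guideline evaluation. Section 4.1 describes infarction as resting on a biomarker rise or fall, with a second troponin 6-9 hours after the first.

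Section 5.2.1 names "Rate of Patients with CABG after Index CA" as a secondary efficacy endpoint, while CABG is also a primary MACE component (5.1) and a secondary safety endpoint (5.2.2). Section 14.2.3 treats measurement bias as implausible because the main outcomes are hard data.

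**The concern.** An infarction still evolving at presentation with a negative first troponin would be picked up by the second sample in a control patient and would count as MACE. The same infarction in a discharged copeptin-negative patient counts only if it later declares itself. Likewise, a planned CABG that follows index angiography is a safety failure in the primary endpoint, yet this group is sent home without index angiography.

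For these two components the endpoint therefore measures intensity of work-up as well as harm. The hypothesis is that the MACE rate is not higher with early discharge. In that kind of comparison, events missed in the experimental arm make a conclusion of safety easier to reach. The reassurance in 14.2.3 does not cover this: an infarction is a firm diagnosis once troponin is repeated, but whether it is repeated depends on the arm and on the copeptin result.

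**Working it through.** The protocol gives no estimate of this effect, so there is no figure to reproduce. Margin, alpha and power are left to an appendix that is not shown; the 446 per arm is not in dispute here.

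**1. Do index events count?** Time zero is admission (section 5), MACE is assessed at discharge (8.6), and neither 5.1 nor 11.1 has an exclusion. The exception in 11.3 concerns only notification of events before the experimental process starts. On the text, index-episode infarction and CABG count. This is an inference; no sentence says so outright.

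**2. Infarctions undetected at discharge, from the cited NPV of 99.7% (4.2, 7.3).**
- Share of arm = copeptin-negative share × (1 − NPV).
- Copeptin-negative share is assumed to be 60-70%.
- 0.60 × 0.3% = 0.18%; 0.70 × 0.3% = 0.21%. That is about 0.2%, or 446 × 0.002 ≈ 1 patient.

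**3. The same from the cited sensitivity of 88.2% at 9.8 pmol/L (7.3).**
- Section 4.1 reports on serial testing: "At baseline, 13.7% of patients were positive for Troponin I, after serial testing this number grew to 26" per cent.
- Implied conversion among baseline-negative patients: (26 − 13.7)/(100 − 13.7) = 12.3/86.3 = 14.3%.
- Lower bound of 5%: assumed, because 6.2 excludes high-risk patients and those with continuing or recurrent pain.
- Share of arm = conversion × (1 − sensitivity): 14.3% × 0.118 = 1.7%; 5% × 0.118 = 0.6%.
- In patients: 446 × 0.006 ≈ 3 to 446 × 0.017 ≈ 8.

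Steps 2 and 3 are ceilings for their inputs, since they suppose that none of these infarctions surfaces within 30 days. If half did (assumed), the figures would halve.

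**4. What such a gap could do to the error rate (illustration only).** Assume a non-inferiority margin M of 5 points, one-sided alpha 0.025, n = 446 per arm, and a true excess equal to M. Let d be the detection gap. The true control rate p0 is set at 6.4% or 7.8%, the reference rates in 14.2.2. Then pT = p0 + M, pC = p0 + d, and

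P(declare safe) = Φ[(M − (pT − pC))/SE − 1.96], with SE = √[pC(1 − pC)/446 + pT(1 − pT)/446].

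| d (points) | P(declare safe) |
|---|---|
| 0 | 2.5% |
| 0.15 | 3.0% |
| 1.0 | 7.0-7.4% |
| 1.75 | 12.9-14.0% |

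This takes d as the net gap, with nothing acting against it.

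**5. What would cancel it.** A control still in the index stay cannot have a re-hospitalisation, and a planned PCI in that stay does not count. A discharged patient who returns with ACS, or for unplanned PCI, does count. If such returns add 0.2% to 1.7% of the arm (about 1 to 8 of 446 patients) who would not have been events as controls, the gap in steps 2-3 is offset in full. The documents give no rate for this.

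**6. CABG.** The protocol has no CABG rate, so only the wording can be tested. One planned operation after index angiography is a primary safety event under 5.1 and an efficacy outcome under 5.2.1; a planned PCI after the same angiogram is not a MACE.

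**The case against.** Several points on the other side stand.

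- **Strategy comparison.** Counting everything from admission is a defensible choice, and index-versus-new rules are often set in a committee charter. An Endpoints Committee exists (5.3). However, the protocol gives it no such rule, and the different treatment of PCI and CABG is in the protocol's own definition.
- **Partial safeguards.** Discharged patients have a final ECG and examination, a cardiologist visit within 3 days (7.1), possibly an optional 3-hour troponin (8.9), and re-admission on suspicion (section 9). It would be too strong to say that their infarctions are never detected, or that every control has angiography. These steps narrow the gap but do not replace systematic serial testing.
- **Weak inputs.** The 14.3% is troponin positivity, not adjudicated infarction, in a general chest-pain-unit population. Section 7.3 does not say whether 88.2% and 94.6% refer to copeptin alone or with troponin.

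A reader might infer three stronger things that the documents do not support:

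1. **That the composite as a whole is biased towards safety.** Working step 5 shows why this is not established.
2. **That 3.2-3.8% of the arm would be missed infarctions**, from 5.4% × 0.60 to 0.70 at the cited NPV of 94.6%. At 88.2% sensitivity this needs an infarction prevalence of 3.2/0.118 to 3.8/0.118, about 27-32%. That is roughly twice the 14.3% implied by 4.1 and above the 244/1293 = 19% in the cohort that supplied the NPV.
3. **That planned CABG is a large part of the bias.** Assuming 1-2% CABG against a 7% MACE rate gives 14-29%, but that is a share of events under an assumed rate, not a difference between arms. Copeptin-positive experimental patients have the same work-up, and the cardiologist may refer discharged patients onward.

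**Conclusion.** The concern holds for the infarction and CABG components. As written, events that standard evaluation detects count from admission, and one group of the experimental arm does not receive that evaluation; for these components this can lower the experimental-arm rate. The PCI/CABG difference in 5.1 and 11.1 needs no numerical assumption.

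For infarction the size runs from negligible (about 0.2% of the arm) to material (0.6-1.7%), against reference MACE rates of 6.4% and 7.8%. This rests on the assumed copeptin-negative share, the assumed 5% lower conversion rate, and accuracy figures carried over from other cohorts. No size can be given for CABG, and no net direction for the whole composite. This is a worthwhile, inexpensive repair to the primary endpoint, not proof that the trial would wrongly declare early discharge safe.

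**What to change.** - In the synopsis, 5.1, 5.2.2 and 11.1, count only unplanned CABG, as is already done for PCI. CABG after index angiography remains visible under 5.2.1.
- Have the Endpoints Committee classify each infarction as index-episode (diagnosed from the presenting troponin series) or new, and report index-episode infarctions separately by arm.
- Keep the analysis that counts all infarctions from admission, and pre-specify beside it a sensitivity analysis of primary MACE without index-episode infarctions.
- Qualify the statement on measurement bias in 14.2.3 accordingly.

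The cost is wording in these sections, one extra eCRF field and slightly fewer primary events. The sensitivity analysis has an opposite asymmetry of its own: a missed infarction that re-presents counts in the discharged group, while the same infarction found by serial troponin in a control drops out. For that reason it should stand beside the all-events analysis, not replace it.

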5.2 Secondary endpoints

5.2.1 Secondary efficacy endpoints

Rate of Patients in whom coronary angiography is performed

Rate of Patients with PCI after Index CA

Rate of Patients with CABG after Index CA

Other cardiovascular diagnoses found in index CA

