Inclusion Criteria	Admission to the Emergency Department with symptoms consistent with ACS: - Typical chest pain (with or without ECG-changes, but no ST-elevation) suggestive of unstable angina or non-ST-elevated myocardial infarction (NSTEMI) - Troponin negative at admission according to the current clinical practice Patient willing and able to give written informed consent
Exclusion Criteria	Patients with ST-elevation myocardial infarction (STEMI) Continuing chest pain or recurrent episodes of chest pain under therapy High-risk patients with suspected ACS who need to be hospitalized for reasons independent of their initial troponin result Patients who need to be hospitalized for other medical reasons Patients in need of urgent life-saving interventions Patients under 18 years of age Patients with a life expectancy < 6 months Patients with any condition that leads the treating physician to not consider the patient eligible for the trial
Study endpoints	Primary Endpoint: Rate of MACE (all- cause death or survived sudden cardiac arrest, myocardial infarction, re-hospitalisation for acute coronary syndrome, acute unplanned PCI, coronary artery bypass grafting (CABG) and documented life-threatening arrhythmias (VF, VT, AV-block III)) within 30 days Copeptin vs. Control group Secondary endpoints: Efficacy endpoint of rate of Patients in whom coronary angiography is performed Rate of Patients requiring PCI due to their findings in cardiac catheterization. Rate of bleeding events at 30 and 90 days defined as non-CABG intracranial, intraocular, or retroperitoneal bleeding; access-site hemorrhage requiring intervention or resulting in a ≥ 5 cm diameter hematoma; reduction in hemoglobin concentration of ≥ 4 g/dL without or ≥ 3 g/dL with an overt bleeding source; reoperation for bleeding; or blood product transfusion. Further secondary endpoints evaluate efficacy, safety, cost effectiveness and patient satisfaction of the new process including length of stay in the hospital
Safety	All major cardiac adverse events (MACE) as defined in the protocol and bleeding complications as defined in the protocol will be assessed and documented for the duration of the study.

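### Coronary angiography and PCI endpoints have no time window, and the follow-up calls do not cover angiography or planned PCI, so procedures deferred after early discharge may be under-recorded mainly in the copeptin arm

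*Protocol*

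**What the plan says.** **Endpoints.** Section 5.2.1 lists "Rate of Patients in whom coronary angiography is performed", "Rate of Patients with PCI after Index CA" and "Rate of Patients with CABG after Index CA". None carries a time window, and *Index CA* is not defined. The synopsis words the PCI endpoint differently, again without a window: "Rate of Patients requiring PCI due to their findings in cardiac catheterization". Elsewhere the protocol does set windows: MACE at 30 and 90 days (5.1, 5.2.2) and, in the synopsis, "Rate of bleeding events at 30 and 90 days".

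**Data collection.** In section 8.7, "Both follow-ups are telephone visits to assess" introduces a list of survival, MACE and bleeding. In the schedule in 8.6, the only item at the 30- and 90-day columns is "MACE and bleeding event assessment"; the table has no row for angiography or PCI at any visit. Section 10.3 describes the calls in the same way. Section 8.7 adds that medical records are requested after a death or hospitalisation during the study.

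**MACE (11.1).** It includes acute unplanned PCI and any CABG. It includes neither coronary angiography nor planned PCI.

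**Patient flow (7.1).** Copeptin-negative experimental patients have no further ACS evaluation in hospital. They see a cardiologist no later than three days after leaving, and then "Further appointments will be at the discretion of the resident cardiologist". Copeptin-positive patients and controls (7.5) receive standard care.

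**The concern.** The intervention can move the decision on angiography from the hospital to the ambulatory sector, and it does so by design in one arm only. If procedures are seen well during the index stay and poorly afterwards, ascertainment depends on the arm. Randomisation does not protect against that. The endpoints committee (5.3) cannot assess procedures that nobody reported.

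The trial sets out to quantify the benefit of adding copeptin. An apparent fall in angiography or PCI would naturally be read as part of that benefit, although some of it could be procedures that took place later and elsewhere.

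**Working it through.** **No plan figure to reproduce.** The protocol gives no expected rate for angiography or PCI. It gives 446 patients per group (2 × 446 = 892), which is used below only as the arm size.

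**Step 1: which post-discharge procedures do the calls cover?**

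| Procedure after discharge | Covered by the 30/90-day items? | Other route |
|---|---|---|
| Diagnostic angiography, outpatient | No | None stated |
| Diagnostic angiography, during an admission | No | Records, if the admission becomes known |
| Planned PCI | No | Records, if there is an admission and it becomes known |
| Acute unplanned PCI | Yes (MACE) | Records |
| CABG | Yes (MACE) | Records |

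The only hospitalisation among the MACE items is re-hospitalisation for ACS, so an elective admission is not a listed item either.

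**Step 2: possible size.** All rates here are assumptions, because the documents give none. Suppose the true 90-day angiography rate R is the same in both arms and in copeptin-negative and copeptin-positive patients, and that controls and copeptin-positive patients defer nothing. Let g be the share of the experimental arm discharged early, d the share of their angiographies deferred to after discharge, and c the share of deferred procedures captured through records.

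Observed experimental rate = R × [1 − g × d × (1 − c)]

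Spurious reduction = R × g × d × (1 − c)

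With d = 0.5:

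| R | g | c = 0 | c = 0.5 | c = 1 |
|---|---|---|---|---|
| 20% | 0.5 | 0.20 × 0.5 × 0.5 = 5.0 points | 2.5 | 0 |
| 30% | 0.5 | 0.30 × 0.5 × 0.5 = 7.5 points | 3.75 | 0 |
| 40% | 0.7 | 0.40 × 0.7 × 0.5 = 14.0 points | 7.0 | 0 |

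**Step 3: chance of a nominally significant false difference** (two-sided 5%, normal approximation, 446 per arm), for R = 30% and g = 0.5:

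- *c = 0:* 30.0% against 22.5%. Pooled standard error √(2 × 0.2625 × 0.7375 / 446) = 0.0295; unpooled 0.0294. (0.075 − 1.96 × 0.0295) / 0.0294 ≈ 0.59, a chance of about 72%.
- *c = 0.5:* 30.0% against 26.25%. Both standard errors are about 0.0301. (0.0375 − 1.96 × 0.0301) / 0.0301 ≈ −0.71, a chance of about 24%.
- *c = 1:* no difference, and the nominal 5%.

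**Step 4: controls may defer too.** Let controls and copeptin-positive patients defer a share k, with R = 30%, g = 0.6, d = 0.5 and c = 0. The gap is R × g × (d − k):

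- k = 0: 0.30 × 0.6 × 0.50 = 9.0 points
- k = 0.25: 0.30 × 0.6 × 0.25 = 4.5 points
- k = 0.50: 0 points

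The bias therefore depends on two quantities that the plan neither states nor measures: the difference in deferral between the arms, and the share captured after discharge.

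**The case against.** **Records are requested after any hospitalisation (8.7).** This stands as a partial safeguard, and it rules out the inference that deferred procedures are simply lost. It leaves outpatient procedures, and admissions that nobody reports because the listed call items do not ask for them.

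**Controls may also be worked up after discharge.** This stands. Section 4.1 names discharge for ambulatory evaluation as one option for troponin-negative patients, and 7.5 requires only guideline care. A reader might assume that every control angiography takes place in hospital, but the protocol does not say so. Greater deferral among copeptin-negative patients is likely from 7.1; its extent is unknown.

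**CABG is collected.** This stands. Since the PCI and CABG endpoints are worded alike, a reader might extend the ascertainment bias to CABG. The calls cover CABG as a MACE component, so the bias argument does not apply to it.

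**Perhaps only the index stay is meant.** The term *Index CA* and the synopsis wording for PCI make this a fair reading. A lower rate would then be a true index-stay result, but it would not show that fewer procedures were done overall. The text does not state the restriction. Nor do the hypotheses in section 5 predict fewer angiographies; that this would be presented as a benefit is inferred from the heading under which the endpoint stands.

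**An analysis plan or the CRF may settle it.** An analysis plan can set a window, but it cannot supply data that were never collected. The CRF is not shown and might hold such an item; the three protocol sections that describe the calls do not call for one.

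**Conclusion.** The point holds as a conditional risk of bias. The angiography and PCI endpoints lack a window, *Index CA* is undefined, and the planned calls do not cover angiography or planned PCI. Early discharge in one arm makes under-recording there the likely direction, which would favour copeptin.

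The documents do not support saying that the trial will show a false reduction. Under the assumed rates above, the effect is 0 if records capture all deferred procedures or if controls defer equally. It is 2.5 to 7 points if half of the early-discharged patients' procedures are deferred and records capture half of those. It is 5 to 14 points if half are deferred, none is captured and controls defer none. These ranges illustrate the mechanism and are not estimates for this trial.

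Only secondary endpoints are affected. The components of the primary 30-day MACE endpoint are collected. A protocol change is advisable because the gap lies in data collection and cannot be closed at analysis.

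**What to change.** 1. Define *Index CA* and use the same PCI wording in the synopsis and 5.2.1.
2. Define the endpoints as any coronary angiography, any PCI (planned or unplanned, inpatient or outpatient) and any CABG, from randomisation to day 30 and to day 90, with all randomised patients of the arm as denominator.
3. Add one question on angiography and PCI to the existing 30- and 90-day calls and to the schedule (8.6, 8.7, 10.3). CABG needs no new question.
4. Use the same wording and the same source of confirmation (procedure report or medical records) in both arms. Do not rely on the co-operating cardiologists for confirmation: sections 7.1 and 9 describe that network for early-discharged copeptin-negative patients, so using it would itself make ascertainment differ by arm.
5. Report index-stay and post-discharge procedures separately as well as together, so that avoided and deferred procedures can be told apart.

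The cost is a small protocol and CRF amendment and one question at calls already planned; patient management does not change. Any apparent reduction in angiography may become less favourable to copeptin.
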